11.4 Electrocardiogram (ECG)

Electrocardiogram (ECG) data will be summarized by treatment group of the antecedent studies, current treatment (SHP465) for each enrollment type, and overall. ECG results and change from baseline will be summarized at each visit and at the FoTA. If there are multiple assessments for the interpretation at any visit, the worst interpretation will be used in the summary tables. For the interval parameters at post-baseline visits, the first readable result will be used if there are multiple assessments.

For the ECG interval parameters, baseline is defined as the average of all valid ECG measurements as the last assessment obtained prior to the first dose of the investigational product. For the ECG interpretation, baseline will be the ECG with the worst interpretation obtained at the baseline Visit (Visit 2), providing this is prior to the first dose of the investigational product.

PCI criteria will be applied to all ECG data at each visit including any repeat/unscheduled assessments and presented by visit. PCI criteria are defined in [Table 10](#) for Age 4-5 years or if they meet the criteria in [Table 11](#) for Age 6-12 years.

Table 10 Criteria for Potentially Clinically Important ECG Values for Age 4-5 Years

ECG Parameter	Unit	Observed Value		Change from Baseline	
		Lower Limit	Higher Limit	Lower Limit	Higher Limit
ECG Result	-	-	Abnormal (core lab) and Clinically significant from investigator	-	-
Heart Rate	Beats/minute	<55	>130	Decrease >15	Increase >15
PR Interval	msec	-	≥200	-	-
QT Interval	msec	-	≥440	-	≥30 and <60 ≥60
QTcF Interval	msec	-	≥440 and <480 ≥480 and <500 ≥500	-	≥30 and <60 ≥60
QTcB Interval	msec	-	≥440 and <480 ≥480 and <500 ≥500	-	≥30 and <60 ≥60
QRS Interval	msec	-	≥90	-	-
Rhythm	-	-	Any rhythm other than sinus rhythm*	-	-

Age is calculated from the informed consent date from antecedent studies for Group A and from the informed consent date from SHP465-308 for Group B.

Table 11 Criteria for Potentially Clinically Important ECG Values for Age 6-12 Years

ECG Parameter	Outlier Criteria
ECG result	Shift from a normal baseline to an abnormal finding or from an abnormal baseline to a new abnormal finding
Heart rate	≤50 beats/minute* or ≥100 beats/minute*
PR interval (increase)	≥200 msec*
QRS interval	≥120 msec*
QTcF/QTcB	≥450 msec* and <480 msec* ≥480 msec* and <500 msec* ≥ 500msec*
QT/QTc from Baseline	≥30 msec* and <60 msec* ≥60 msec*

*The NCI has not specified a value, Shire physicians have agreed on values provided.

ECG=electrocardiogram; QTcB=Bazett's corrected QT interval; QTcF=Fridericia's corrected QT interval

Age is calculated from the informed consent date from antecedent studies for Group A and from the informed consent date from SHP465-308 for Group B.

The number and percentage of subjects with post-baseline PCI values will be tabulated. The percentages for the observed value criteria will be calculated relative to the number of subjects with at least 1 post-baseline assessment available per parameter and visit. The percentages for the change from baseline criteria will be calculated relative to the number of subjects with available baseline and at least 1 post-baseline assessment per parameter and visit. The numerator is the total number of subjects with at least 1 PCI post-baseline ECG value.

Additionally, a summary table showing the number and percentage of subjects with the Central Reader's assessment of the ECG result as normal, abnormal or unable to evaluate, and the investigator's assessment of abnormal ECG results as not clinically significant or clinically significant at each visit and at the FoTA will be produced. A shift table showing the change in evaluation from baseline to the FoTA will also be produced.

Listings of ECG data including the central reader's assessment and investigator's interpretation by individual subject will be produced. Separate listings will be produced for subjects with ECG results meeting the PCI criteria. Data from unscheduled visits will be listed, but not summarized.

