**Table 2: Schedule of Assessments for Group B**

Period	Screening/ Washout a		Baseline	Treatment Period														1-Week Safety Follow-up
	1	Phone call		2	3	4	5	6	7	8	9	10	11	12	13	14	15	16/ET c
Assessment Week/Month	-5 to -1	-1	0	W1	W2	M1	M2	M3	M4	M5	M6	M7	M8	M9	M10	M11	M12	W53
Assessment Day b	-32 to -3	-7	0	7	14	30	60	90	120	150	180	210	240	270	300	330	360	367

e Medical history will include all lifetime psychiatric and nonpsychiatric medications and procedures.

f Whenever possible, the same individual should complete/rate consistently the following scales and questionnaires as appropriate: ADHD-RS-5, CGI-S/I, and subject check to remain in the study; PSQ and CSHQ. Include assessment of decreased appetite.

g If >32 days have elapsed since the screening evaluation was completed at Visit 1, then the following evaluations must be repeated at baseline (Visit 2): vital signs, clinical laboratory evaluations, and ECGs in triplicate. The physical examination will be abbreviated with a review of the following body systems: general appearance, respiratory, and cardiovascular.

h Height and weight will be measured without shoes and with light clothing using a stadiometer for height and calibrated scale for weight.

i For females of child-bearing potential only

j Vital signs include oral or tympanic temperature, pulse, sitting blood pressure, and respiratory rate. The subject will have been seated for a minimum of 3 minutes before blood pressure, pulse, and respiratory rate measurements are taken. Measurement of blood pressure and pulse will be collected 3 times (with at least 2 minutes in between each collection) using the age-appropriate cuff.

k Blood pressure and pulse rate will be measured at each study visit. Temperature and respiratory rate will be measured at screening (Visit 1) only.

l Clinical laboratory evaluations will include hematology, biochemistry, endocrinology, and urinalysis.

m ECGs will be recorded in triplicate with at least 3 minutes in between each collection at screening only and at baseline only if >32 days have elapsed since the screening evaluation was completed at Visit 1.

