## 1.2 Product Background and Clinical Information

SHP465 and its prototypes have been evaluated in 1641 subjects in 16 clinical studies, of which 13 clinical studies were in adult subjects aged 18 to 55 years and 3 clinical studies were in pediatric subjects aged 6 to 17 years. The SHP465 clinical development program has shown that doses of 12.5 to 50 mg in adult subjects and 12.5 to 25 mg in pediatric subjects demonstrate a safety and efficacy comparable to the profile reflected in class labeling for stimulant products approved in the United States (US).

The pharmacokinetic (PK) profile of SHP465 is not affected if the capsule is consumed intact or if capsule contents are sprinkled onto a small amount of food (ie, 1 tablespoon of applesauce) and then ingested. The PK properties of SHP465 are not affected by sex or race. The PK properties between *d*- and *l*-amphetamine are similar.

Acceptable safety and tolerability profiles observed were consistent with the types of side effect specified in stimulant class labeling in the US. Specifically, administration of SHP465 was associated with increases in blood pressure (mean increase approximately 2-4 mmHg) and heart rate (mean increase approximately 3-6 bpm), and treatment-emergent adverse events (TEAEs) of insomnia, decreased appetite, decreased weight, heart rate increased, and anxiety, as well as psychiatric events (eg, mania, suicidality).

Always refer to the latest version of the SHP465 Investigator's Brochure (IB) for the overall risk/benefit assessment and the most accurate and current information regarding the drug metabolism, PK, efficacy, and safety of SHP465.

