**Figure 1: Study Design Flow Chart for Group A**

**Figure 2: Study Design Flow Chart for Group B**

### 3.2 Duration and Study Completion Definition

Each subject's maximum duration of participation is expected to be approximately 12 months. The study will be completed in approximately 18 months.

Planned duration of screening/washout:

- For Group A (subjects from antecedent studies): None
- For Group B (directly enrolled subjects): up to 32 days

Planned duration of treatment:

- For Group A (subjects from antecedent studies): 12 months, baseline visit procedures will be used to confirm subject eligibility for this study
- For Group B (directly enrolled subjects): 12 months

Planned duration of safety follow-up:

- For Group A (subjects from antecedent studies): 7 days
- For Group B (directly enrolled subjects): 7 days

The study completion date is defined as the date the final subject, across all sites, completes their final protocol-defined assessment. Please note that this includes the follow-up visit or contact, whichever is later. The study completion date is used to ascertain timing for study results posting and reporting.

Subjects in both age groups will be treated and evaluated for 12 months and visit the site up to 15 times for subjects in Group A and up to 16 times for subjects in Group B.

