**Table 3: Common Excluded Treatments and Associated Washout Period - Relative to Baseline Visit (Visit 2)**

Treatment	Minimum Number of Days Before Baseline Visit		
	7	14	30
Psychostimulants, amphetamines, and amphetamine-like agents	X		
Antihypertensives a	X		
Antihistamines (centrally and peripherally active)		X	
Herbal preparations (including melatonin)		X	
Sedatives, anxiolytics, antipsychotics a			X
Monoamine oxidase inhibitors a			X
Antidepressants a			X
Clonidine and guanfacine			X
Selective noradrenaline reuptake inhibitors and noradrenaline reuptake inhibitors a			X
CYP2D6 inhibitors (eg, paroxetine, fluoxetine, quinidine, ritonavir)			X
Alkalinizing agents (eg, sodium bicarbonate, acetazolamide, some thiazides)			X
Acidifying agents (eg, guanethidine, reserpine, glutamic acid HCl, ascorbic acid, ammonium chloride, sodium acid phosphate, methenamine salts)			X

a These medications may signal that an exclusionary diagnosis is present. The medical monitor should be consulted before instructing a subject to discontinue 1 of these medications for this study.

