#### 7.1.1.1 Screening Visit (Visit 1) for Group B

Subjects in Group B will be screened at Visit 1 to establish eligibility for study participation.

Table 2 (Group B) details all procedures to be completed at the screening visit (Visit 1) and should serve as the primary point of reference regarding study procedures. Additional clarification on the procedures performed during the screening visit (Visit 1) is as follows:

- Eligibility will be established per inclusion and exclusion criteria, including documentation of any prior nonpharmacological treatment, specified MINI-KID, and C-SSRS criteria. Areas of impairment will be recorded for all subjects for assessing the severity of the subject's condition.
- All adverse events (AEs) occurring after signature of informed consent must be recorded in the source documents.
- Three 12-lead ECGs will be taken, with approximately 3 minutes in between each one, to ensure that appropriate baseline intervals are established. The investigator will perform the initial interpretation of the ECG immediately after collection to ensure the safety of each subject. The ECG tracing will be sent to the central reader for analysis. Upon review of the report from the central reader, the investigator will re-evaluate the clinical significance of the ECG in light of other safety data for the subject. If abnormal and significant results are observed following assessment by the central reader, the investigator, in consultation with the appointed CRO medical monitor, will confirm the subject's eligibility to participate in this study.
- Vitals will include oral or tympanic temperature, pulse, sitting blood pressure, and respiratory rate. Also, blood pressure and pulse will be collected 3 times (with at least 2 minutes in between each collection) using the age-appropriate cuff during the visit. The average of each set of 3 measurements will be used to determine continued participation in the study (see Section 4.3.1).
- Height and weight will be measured without shoes.
- The "baseline" version of the Pediatric/Cognitively Impaired Version C-SSRS should be completed.
- Clinical lab tests will include hematology, biochemistry, endocrinology, and urinalysis.
- Historical/concomitant medications will be recorded as follows:
  - All lifetime psychoactive medications and lifetime nonpharmacological interventions (behavioral therapy) for ADHD
  - Other medications used during the 30 days before the screening visit (Visit 1)

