#### **7.1.1.2 Washout Telephone Call (Group B)**

The washout period will be initiated after clinical laboratory test results and 12-lead ECG results have been received and reviewed by the investigator.

Eligible subjects will be contacted by a member of the site staff and provided with instructions on discontinuing any protocol-prohibited medications. During washout, a subject's current prohibited medications (if applicable) will be discontinued for a period of up to 32 days or 5 times the half-life of the medication, whichever is longer. Washout periods for prohibited medications are defined in [Table 3](#).

As part of the washout telephone call, site personnel will perform the following procedures:

- Schedule the baseline visit (Visit 2)
- Review the inclusion/exclusion criteria
- Ask about any concomitant medications that the subject is taking. If new concomitant medications that require washout are noted, instructions for appropriate washout will be provided
- Provide instructions on discontinuing any medication requiring washout
- Determine if any AEs have occurred since the screening visit (Visit 1)

If a medication washout is not necessary, the washout telephone call will include all the above procedures except providing instructions on discontinuing any current medications.

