11. SAFETY ANALYSES

Safety data will be analyzed for the Safety Set by treatment group of the antecedent studies, current treatment (SHP465) for each enrollment type, and overall. Safety endpoints include the occurrence of TEAEs, vital signs (systolic and diastolic blood pressure, and pulse), height, weight, body mass index (BMI); clinical laboratory and ECG results, C-SSRS, and sleep questionnaires (PSQ and CSHQ). For each safety endpoint, the last value collected before the first dose of investigational product in this study will be used as baseline for all analyses of that safety endpoint. Except for adverse event data, only post-baseline assessments from Visit 2 (Week 0) up to Visit 16 (Month 12) that were collected on or 2 days after the last dose of investigational product will be analyzed. A Final on-Treatment Assessment (FoTA) will be defined as the last valid assessment obtained after Baseline and whilst on investigational product (on or before 2 days after the last dose date).

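### Group B children on a stimulant at screening normally get an on-stimulant ECG baseline, so their ECG heart-rate change is a drug-to-drug comparison

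*SAP*

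**What the plan says.** **Baseline.** For ECG interval parameters, SAP 11.4 states that "baseline is defined as the average of all valid ECG measurements as the last assessment obtained prior to the first dose" of study drug. The general rule in SAP 11 agrees: "the last value collected before the first dose of investigational product in this study will be used as baseline". Whichever rule covers ECG heart rate, its baseline is the last pre-dose ECG.

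**Timing in Group B.** Protocol 7.1.1.1 takes triplicate ECGs at Visit 1 "to ensure that appropriate baseline intervals are established". Protocol 7.1.1.2 then says: "The washout period will be initiated after clinical laboratory test results and 12-lead ECG results have been received and reviewed by the investigator". Table 2, footnote m, has triplicate ECGs recorded "at screening only and at baseline only if >32 days have elapsed since the screening evaluation was completed at Visit 1"; sections 7.1.1.4 and 7.2.3.8 say the same. The planned length of screening and washout in Protocol 3.2 is "For Group B (directly enrolled subjects): up to 32 days".

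**Who may be on a stimulant.** Protocol 5.2.2 allows a medicine to be stopped for the study only after consent. Table 3 puts "Psychostimulants, amphetamines, and amphetamine-like agents" in the 7-day column. Inclusion criterion 5 has a route for children aged 6-12 who are not fully satisfied with current ADHD therapy. Exclusion criterion 21 exempts a current ADHD stimulant on the urine drug screen.

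**Pulse.** The Visit 2 vital-signs entry in Table 2 carries the 32-day footnote. However, footnote k and sections 7.1.1.4 and 7.2.3.4 have blood pressure and pulse taken at every site visit, so at Visit 2 in every case.

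**The concern.** Followed exactly, the plan gives some Group B children a baseline ECG recorded while they were taking another stimulant. Their next scheduled ECG comes after SHP465 has started. Their ECG heart-rate change is then the SHP465 effect minus the earlier drug's effect, and a value near zero cannot be told apart from a true absence of effect.

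ECG results are part of the primary safety objective (Protocol 2.2.1, SAP 3.1). The vital-signs table will show the same children's pulse change from a post-washout value. The two tables can therefore disagree for a reason unrelated to SHP465, and nothing in the SAP warns the reader. Group B also feeds the Total column (SAP 2.1).

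The protocol recognises that washout changes a child's drug state between the two visits. Section 7.2.3.6 requires a Visit 1 drug screen made positive by a prescribed medicine to be repeated, and to be negative, at Visit 2. The ECG rule depends only on elapsed time.

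**Working it through.** The documents give no figure for this point, so there is none to reproduce. The check covers the timing, then the possible size.

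**1. Timing**

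Inputs: repeat threshold of more than 32 days (Table 2, footnotes g and m); minimum washout of 7 days for stimulants and 30 days for several other classes (Table 3).

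- Stimulant only: 32 − 7 = 25 days of slack, so normally no repeat ECG.
- 30-day medicine: 32 − 30 = 2 days of slack. Washout starts only after laboratory and ECG results are back, so a repeat is likely.

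The planned period is itself at most 32 days, so a repeat occurs only when the planned period is exceeded.

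**2. Size for ECG heart rate**

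Let *d* be the SHP465 effect against an off-drug state, *h* the earlier stimulant's effect present at the Visit 1 ECG, and *p* the share of Group B on a stimulant at that ECG.

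- Measured change in an affected child = *d* − *h*
- Shortfall in the Group B mean = *p* × *h*

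The documents give neither *p* nor *h*. For *h* I assume 3-6 bpm, from Protocol 1.2: "heart rate (mean increase approximately 3-6 bpm". That describes SHP465, in a programme of 12.5-50 mg in adults and 12.5-25 mg in pediatric subjects. It does not describe the earlier drug or the 6.25 mg dose. For *p* I show 25% to 75%.

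| *p* | *p* × 3 bpm | *p* × 6 bpm |
|---|---|---|
| 25% | 0.75 | 1.5 |
| 50% | 1.5 | 3.0 |
| 75% | 2.25 | 4.5 |

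If *d* and *h* both lie in 3-6 bpm, an affected child shows between 3 − 6 = −3 and 6 − 3 = +3 bpm, instead of +3 to +6.

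**3. Criteria for potentially clinically important (PCI) values**

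- Heart-rate change of more than 15 bpm appears only in SAP Table 10 (ages 4-5). An on-stimulant baseline makes the increase harder to reach and the decrease easier.
- QT/QTc change of ≥30 and ≥60 msec appears in Tables 10 and 11.
- PR and QRS have no change criterion. Observed-value criteria do not use the baseline.

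To illustrate the 15 bpm increase, take change as normal with mean *d* = 3-6 bpm from an off-drug baseline and mean 0 when *d* = *h*. The SD is not in the documents; 8-12 bpm is assumed. P(increase > 15) = 1 − Φ((15 − mean)/SD).

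| SD | Off-drug baseline | On-stimulant baseline, *d* = *h* |
|---|---|---|
| 8 | 6.7-13.0% | 3.0% |
| 10 | 11.5-18.4% | 6.7% |
| 12 | 15.9-22.7% | 10.6% |

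**4. Direction for intervals**

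The documents give no stimulant effect on PR, QRS or QTc. Uncorrected QT shortens as heart rate rises. If the earlier stimulant raised heart rate, baseline QT would be short, and a later increase of 30 or 60 msec could be easier to reach.

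**The case against.** The timing is not in dispute; the case against concerns how much follows from it.

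- **Intervals.** A reader might infer that all ECG change is understated. The documents do not support that. Only heart rate has a stated stimulant effect, and uncorrected QT could be biased the other way. This objection stands.
- **Size.** A reader might infer that a quarter to three quarters of the SHP465 effect is lost. Once *h* is set equal to *d*, the fraction lost is simply the assumed share, so that figure carries no information. This stands too. In addition, the analysis is descriptive with no tests (SAP 2.6), so power is not at issue.
- **Who is affected.** The current-therapy entry route is for ages 6-12, while the 15 bpm criterion is for ages 4-5. Current therapy need not be a stimulant. Exclusion criterion 11 removes children who did not fully respond to amphetamine, so an earlier amphetamine is less likely. This narrows the affected group but does not empty it: exclusion 21 has no age limit, and Protocol 1.1 counts methylphenidate as a stimulant.
- **Existing safeguards.** Group B has its own column, pulse change starts after washout, and medication histories and ECGs are listed. These let a reader identify affected children one by one. They do not correct the summary tables.
- **Early termination.** The sponsor ended the study on 14 December 2018 (SAP 1), so the visit schedule can no longer change for these children. The analysis still can.

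**Conclusion.** The point holds for ECG heart rate in Group B children who were taking a stimulant at Visit 1 and reached Visit 2 within 32 days. Their change from baseline is a drug-to-drug comparison, biased toward no change provided the earlier stimulant raised heart rate. For PR, QRS, QT and QTc the baseline is contaminated, with no direction that the documents support.

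The size is unknown. The shortfall in the Group B mean is 3-6 bpm times an unreported share, on a borrowed effect size; 0.75-1.5 bpm at 25% and 2.25-4.5 bpm at 75% are illustrations, not estimates. The timing finding needs neither assumption. Children not on a stimulant at Visit 1, children with a repeat ECG after washout, blood pressure, pulse and observed-value ECG criteria are not affected by this problem.

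**What to change.** In SAP 11.4, using data already collected:

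- Flag each Group B child with a stimulant or other Table 3 medicine ongoing at the ECG used as baseline, from the recorded medication dates (history under Protocol 7.1.1.1; SAP 7.2, 9 and 18.6). Where a partial stop date leaves this open, flag the child.
- Present ECG change from baseline and the change-based PCI criteria separately for flagged and unflagged Group B children.
- Base the Group B off-drug ECG conclusion on the unflagged children, and state the limitation for the flagged.
- Cite the existing Visit 2-based pulse change as supportive evidence only. A reader might be tempted to use Visit 2 pulse as the heart-rate baseline, but that would subtract a seated vital-sign reading from an ECG heart rate and mix two methods in one change score.

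The cost is one extra table and smaller subgroups; no new data are needed.

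For any later protocol, the 32-day repeat rule (Table 2 footnotes g and m, 7.1.1.4, 7.2.3.8) and the washout sequence in 7.1.1.2 should be reconciled with the purpose that 7.1.1.1 gives for the triplicate ECGs. How to do so is a matter for the sponsor.

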f Blood pressure and pulse rate will be measured at each study visit. Temperature and respiratory rate will be measured at baseline (Visit 2).

g Height and weight will be measured without shoes and with light clothing using a stadiometer for height and calibrated scale for weight.

h Clinical laboratory evaluations will include hematology, biochemistry, endocrinology, and urinalysis.

i Electrocardiograms will be recorded in triplicate with at least 3 minutes in between each collection at baseline only.

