#### 7.1.1.4 Baseline Visit (Visit 2) Group B

Once the screening central clinical laboratory tests and 12-lead ECG results have been obtained, in addition to repeat assessments (if required), and the subject has completed the required washout period (if applicable), the subject will return to the site for the baseline visit (Visit 2).

Inclusion/exclusion criteria must also be reviewed during this visit to ensure that the subject continues to meet all eligibility criteria.

Table 2 (Group B) outlines all procedures to be conducted during the baseline visit (Visit 2) and should serve as the primary point of reference regarding study procedures. Additional clarification on the procedures performed during the baseline visit (Visit 2) is provided as follows:

- For subjects with >32 days since the safety measurements at the screening visit (Visit 1) were collected, an abbreviated physical examination, vital signs, clinical laboratory tests, and 12-lead ECG in triplicate must be repeated, and the results reviewed by the investigator before the subject is enrolled.
- Blood pressure and pulse will be collected 3 times (with at least 2 minutes in between each collection) using the age-appropriate cuff during the visit. The average of each set of 3 measurements will be used to determine continued participation in the study (see Section 4.3.1).
- If >32 days since the screening visit (Visit 1), 3 ECGs will be taken, with approximately 3 minutes in between each one, to ensure that appropriate baseline intervals are established. The investigator will perform the initial interpretation of the ECG immediately after collection to ensure the safety of each subject to continue with the study. The ECG tracing will be sent to the central reader for analysis. Upon review of the report from the central reader, the investigator will re-evaluate the clinical significance of the ECG in light of other safety data for the subject. If abnormal and significant results are observed following assessment by the central reader, the investigator, in consultation with the appointed CRO medical monitor, will

confirm the subject's continued participation in this study.

- The C-SSRS "Since Last Visit" Version of the Pediatric/Cognitively Impaired Version should be completed.

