#### **7.2.3.8 Electrocardiogram**

A 12-lead ECG will be performed as per schedule of assessments [Table 1](#) (Group A) and [Table 2](#) (Group B). Additionally, for subjects in Group B, a 12-lead ECG is required to be repeated before the baseline visit (Visit 2), and the results reviewed before enrolling the subject in the study, if >32 days have elapsed since the 12-lead ECG completed as part of the screening visit (Visit 1) was performed. Additional ECGs may be performed during the study at the investigator's discretion. Electrocardiograms will be recorded in triplicate with approximately 3 minutes apart at the screening visit or baseline visit for Group B.

All ECGs will be performed after 3 minutes of rest using the central ECG provider's equipment and will be sent to the central ECG provider electronically.

The initial interpretation of the ECG, normal or abnormal and clinical significance, will be performed immediately after collection to ensure the safety of each subject. An ECG tracing will then be evaluated by a cardiologist at a central ECG reading vendor and returned to the site with a determination of normal or abnormal. Upon review of the report from this vendor, the investigator will re-evaluate the clinical significance of the ECG while taking into consideration all other safety data available for the subject.

Although a central ECG reader is being used for this study, the eligibility of the subject is based on the investigator's assessment of the ECG. If abnormal and significant results are observed following assessment by the central reader, the investigator, in consultation with the appointed CRO medical monitor, reconfirms subject eligibility to continue.

All ECGs transmitted to the central ECG reader will be analyzed. If the central ECG reader receives multiple ECGs, the first readable ECGs will be analyzed as the scheduled ECG. Every ECG transmitted to the central ECG reader will have corresponding source document data collected. No ECG should be deleted by study site personnel. All ECGs must be transmitted to the central provider regardless of quality, results, or number of ECGs taken at a respective visit.

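### SAP 11.4 ties the baseline ECG interpretation to Visit 2, so a Group B subject who reaches Visit 2 within 32 days of screening has, read literally, no interpretation baseline

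*SAP*

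**What the plan says.** SAP 11.4 has two baseline rules for ECG data, in adjacent sentences.

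- **Rule for intervals.** The SAP states: "baseline is defined as the average of all valid ECG measurements as the last assessment obtained prior to the first dose". No visit is named.
- **Rule for the interpretation.** The SAP states: "baseline will be the ECG with the worst interpretation obtained at the baseline Visit (Visit 2), providing this is prior to the first dose". Visit 2 is named and no fallback is given.

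SAP Section 11 sets the general rule for safety data: "the last value collected before the first dose of investigational product in this study will be used as baseline for all analyses". SAP 18.4 adds that, when pre-dose assessments are repeated, the final one before the start of product is baseline.

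For Group B, footnote m of Table 2, in both documents, says that triplicate ECGs are recorded "at screening only and at baseline only if >32 days have elapsed since the screening evaluation was completed at Visit 1". Protocol 7.1.1.4 repeats the condition: "If >32 days since the screening visit (Visit 1), 3 ECGs will be taken". Protocol 3.2 gives the planned screening and washout length: "For Group B (directly enrolled subjects): up to 32 days".

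For Group A, footnote i of Table 1 reads: "Electrocardiograms will be recorded in triplicate with at least 3 minutes in between each collection at baseline only".

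**The concern.** The interpretation rule looks for an ECG at a visit where most of the plan's own logic says Group B need not have one. The SAP reproduces the conditional footnote in its own Table 2, so the conflict lies within that document as well as between the two.

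ECG results are part of the primary safety objective. The final analysis will use all collected data despite the early termination described in SAP Section 1. Outputs that compare a later interpretation with baseline need a baseline category for each subject. If the sentence is programmed as it stands, some directly enrolled children drop out of those comparisons even though a usable screening ECG is on file. If Section 11 is programmed instead, they stay in. Two careful programmers could therefore produce different tables from the same data.

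**Working it through.** No sample size or power figure is involved. The check compares the schedule with the definitions.

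**Step 1: when does a Group B subject have a Visit 2 ECG?**
- Protocol Table 2 puts Visit 1 on Day -32 to Day -3 and Visit 2 on Day 0. The tabulated gap is therefore 3 to 32 days.
- The repeat requires more than 32 days, that is, at least 33.
- Since 32 > 32 is false, a subject inside the tabulated window has no scheduled Visit 2 ECG. The last scheduled pre-dose ECG is the screening triplicate.

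**Step 2: can the gap exceed 32 days under the protocol?** Yes.
- Protocol 7.1.1.2 starts washout only after the laboratory and ECG results have been reviewed. It allows washout to last up to 32 days or 5 half-lives, whichever is longer.
- Protocol Table 3 sets minimum washouts of 7, 14 or 30 days.
- Let *t* be the days from Visit 1 to the start of washout. The documents do not give it, so it is an assumption. With the minimum washout, the gap reaches 33 days when *t* is at least 33 - 30 = 3, 33 - 14 = 19 or 33 - 7 = 26 days.
- A subject on a 30-day washout could therefore pass the trigger easily. A subject with a short washout or none would pass it only after a long delay.

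**Step 3: what does each rule give?**

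| Group B subject | SAP 11.4 interpretation rule, read literally | Section 11, interval rule, 18.4 |
|---|---|---|
| Gap of 32 days or less, ECG at Visit 1 only | No baseline | Visit 1 ECG |
| Gap over 32 days, repeat recorded at Visit 2 | Visit 2 ECG | Visit 2 ECG |
| Gap over 32 days, repeat dated before Visit 2 | No baseline | The repeat ECG |

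The third row is marginal. Protocol 7.2.3.8 asks for the repeat before the baseline visit, whereas Protocol 7.1.1.4 and the Table 2 footnotes place it at that visit.

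**Step 4: which outputs use an interpretation baseline?**
- The shift table from baseline to the final on-treatment assessment (SAP 11.4): an affected subject has no baseline category.
- The *ECG result* criterion in SAP Table 11 (ages 6-12), which is defined as a shift from baseline: an affected subject cannot meet it.
- Any baseline row of the by-visit table of central-reader and investigator assessments: an affected subject is absent from it.

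Interval changes, observed-value interval criteria, the *ECG Result* criterion in Table 10 (ages 4-5, observed value only), post-baseline rows and listings do not use it.

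**Step 5: effect on the Table 11 percentage.** SAP 11.4 gives one denominator for observed-value criteria and another for change-from-baseline criteria. Table 11 does not say which applies to this row. Let *f* be the share of Group B subjects aged 6-12 without a Visit 2 interpretation and *p* the shift rate, assumed equal with and without one. Both are unknown.
- Change-from-baseline denominator (the more natural reading): the percentage stays at *p* but rests on the fraction 1 - *f* of subjects.
- Observed-value denominator: the percentage becomes (1 - *f*)*p*, for example 0.75*p* at *f* = 0.25 and 0.50*p* at *f* = 0.50.

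This shows the direction only. It does not estimate a size.

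**The case against.** The strongest reply is that Section 11 already covers the case. It sets the last pre-dose value as baseline for all analyses of a safety endpoint, ECG results are a listed endpoint, and 18.4 points the same way. On this view the 11.4 sentence only says which of several interpretations to use, namely the worst, and does not discard the only pre-dose ECG. That is probably what was intended, and a programmer may well do it. It does not remove the explicit mention of Visit 2, which stands directly after a sentence that names no visit. A specific rule is ordinarily read as overriding a general one. Table specifications are in a separate document, so the implementation cannot be checked here.

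A reader might infer that no Group B subject can have a Visit 2 ECG, or that the repeat condition can never be met. The documents do not support that: step 2 shows that longer gaps are allowed, and Protocol 7.2.3.8 also permits additional ECGs at the investigator's discretion.

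Two further points limit the consequence. Analyses are descriptive, with no formal tests, and all ECG data are listed. Exclusion criterion 13 bars clinically significant ECG abnormalities, so the baseline category of abnormal and clinically significant should be almost empty. The distinction between normal and abnormal but not clinically significant remains, and the Table 11 criterion turns on it.

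For Group A, the Table 1 triplicate supplies a Visit 2 ECG, so no baseline is lost. However, SAP 2.1 says that the antecedent study's baseline serves as Visit 2 for analyses. Which ECG the term Visit 2 denotes for Group A is therefore not beyond doubt, and the replacement wording should settle it.

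**Conclusion.** The sentence is wrong as written, and the matter is minor. For a Group B subject whose gap from Visit 1 to Visit 2 is 32 days or less, which is the planned length, the stated rule gives no interpretation baseline although a screening ECG exists. The other three SAP rules would supply one. Subjects with a longer gap are generally not affected.

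The effect is limited to the descriptive outputs in step 4. The number of subjects cannot be computed, because the documents give neither the size of Group B nor its screening intervals. A reader might infer that data will certainly be lost or that the Table 11 percentage will be biased. Neither follows: under Section 11 as the default no subject is lost, and under the change-from-baseline denominator with a common shift rate the percentage is unchanged on fewer subjects. What is established is a conflict between stated rules, which leaves these outputs dependent on which sentence is programmed.

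**What to change.** Replace the interpretation sentence in SAP 11.4 with:

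> For the ECG interpretation, baseline is the worst interpretation among the ECGs recorded at the last assessment before the first dose of investigational product in this study (SHP465-308), whichever visit that assessment belongs to.

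This agrees with Section 11, the interval rule and 18.4, and it covers a repeat ECG dated before Visit 2. The words *in this study* are needed because some Group A subjects had already taken SHP465 in an antecedent study. For Group A, the wording selects the last ECG before SHP465-308 dosing, normally the one at Visit 2. If the sponsor has been reading Visit 2 through SAP 2.1 as the antecedent study's own baseline, Group A's interpretation baseline would change, and the sponsor should confirm which was meant.

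The cost is one SAP sentence and one derivation line, using ECGs already collected. A subject whose only pre-dose ECG set in this study is at Visit 2, or whose repeat was recorded there, keeps the same baseline.
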